5.11 Subgroup Analysis of Immunogenicity/Efficacy Data

Subgroup analysis by APOE4 carrier will be performed for all immunogenicity and efficacy data, and the analysis model will be the same as the overall analysis.

5.12 Analysis of Safety Data

5.12.1 General

The review of safety and tolerance will be performed on the safety population as defined in Section 5.3.2 Safety Population.

The observation period will be divided into 2 segments: pre-treatment and post-treatment.

- The pre-treatment period is defined as the time from the date of the informed consent to the time before the administration of first dose of study medication.
- The post-treatment period is defined as the time from after the first dose of study medication to the end of the study.

The summary of safety results will be presented by each treatment group.

5.12.2 Adverse Events

Pre-treatment AEs are defined as AEs that develop or worsen or become serious during the pre-treatment period.

Treatment-emergent AEs (TEAEs) are defined as AEs that develop or worsen (according to the investigator’s judgement) or become serious during the post-treatment period.

The primary focus of adverse event reporting in the CSR will be TEAEs. Pre-treatment AEs will be described separately.

All adverse events

All adverse events are to be coded to a “Preferred Term” and primary “System-organ Class” using the Medical Dictionary for Regulatory Activities (MedDRA).

Summaries of all TEAEs by subjects and events in each treatment group, will include:

- The overview of AEs, summarizing number (n) and percentage (%) of subjects with any TEAE/serious TEAE.
- The number and percentage of subjects with at least one TEAE by System-organ Class and Preferred Term.
- Summary of TEAEs by intensity (Grades 1 to 5), presented by System-organ Class and Preferred Term.
- Summary of TEAEs by causal relationship to the study drug, by System-organ Class and Preferred Term.

Serious adverse events

Serious TEAEs will be summarized and presented as number and percent of subjects and events in each treatment group.

Adverse events leading to treatment discontinuation

TEAEs leading to treatment discontinuation will be summarized and presented as number and percentage of subjects and events in each treatment group.

Local tolerability at injection site

The number and percentage of subjects and events with reaction at injection site will be summarized and presented by treatment group

5.12.3 Clinical Laboratory Assessments

The summaries will include subjects in the safety population with at least one laboratory test

performed during the post-treatment period and, when required by the definition of the abnormality, with an available baseline value and available laboratory normal ranges. For those descriptions, the baseline value will be the last available measure before the first study drug injection.

Descriptive statistics will be used to summarize the laboratory results and the changes from baseline by scheduled visit for each treatment group. Laboratory results will be listed.

5.12.4 Vital Signs

The summaries will include subjects in the safety population who have at least one parameter to be analyzed during the post-treatment period. Descriptive statistics will be used to summarize the results and the changes from baseline value by scheduled visit for each treatment group. The listing will be provided for vital signs data.

5.12.5 12-lead ECG Status

Only ECG status (i.e. normal or abnormal) will be reported. Descriptive statistics will be used to summarize the ECG status and the changes from baseline by scheduled visit for each treatment group. The listing will be provided for ECG data.

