## 7 ASSESSMENT OF SAFETY

### 7.1 Safety Endpoints

- Local tolerability at the injection site
- Amyloid-related imaging abnormalities (ARIA) including vasogenic edema and/or sulcal effusion (ARIA-E) and hemosiderin deposits (ARIA-H), such as microhemorrhage and superficial siderosis.
- Other adverse events and serious adverse events
- Vital signs
- Physical examination
- 12-lead Electrocardiogram (ECG)
- Laboratory tests: hematology, clinical chemistry, and inflammatory parameters

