#### 7.1.4 ECG

A 12-lead ECG record is performed at the first screening (S1) and at Weeks 52 (V10) and 78 (V13). The 12-lead ECGs should be performed after at least 10 minutes in supine position. The electrodes are to be positioned at the same place for each ECG recording.

Both traces will be analyzed in comparison with the screening recorded trace at the end of the study. The original trace is kept as source data. In the CRF the assessment “normal”, “abnormal-clinically significant”, or “abnormal- not clinically significant” as determined by the investigator, is collected.

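### The ECG is graded in three categories but summarised in two, so the by-arm change table shows a move between not clinically significant and clinically significant as no change (minor)

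*SAP*

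**What the plan says.** Protocol 7.1 lists the 12-lead ECG among the safety endpoints, and Protocol 9.2.4 and SAP 4.4 repeat it among the safety variables. Under Protocol 7.1.4 it is recorded at the first screening visit and at Weeks 52 and 78. The CRF takes one of three investigator assessments: normal, "abnormal-clinically significant”, or “abnormal- not clinically significant” as determined by the investigator, is collected". The same section plans a comparison over time: "Both traces will be analyzed in comparison with the screening recorded trace at the end of the study".

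The analysis sections use two levels. Protocol 9.4.5.4 and SAP 5.12.5 carry the same sentence: "Only ECG status (i.e. normal or abnormal) will be reported". SAP 5.12.5 adds two things: "Descriptive statistics will be used to summarize the ECG status and the changes from baseline by scheduled visit for each treatment group", and "The listing will be provided for ECG data". It does not say which columns the listing will hold.

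**The concern.** The grade that separates an incidental finding from one the investigator considers important is collected and then dropped from the only planned by-arm ECG summary. A subject with a minor abnormality at screening and a clinically significant trace at Week 52 is abnormal both times, so the summary records no change. A subject who goes from normal to a trivial abnormality is counted as changed, in the same cell as one who goes from normal to clinically significant.

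Safety and tolerability is a primary endpoint, and there are only two scheduled post-baseline ECGs. The inclusion and exclusion criteria (Protocol 4.2 and 4.3) do not mention the ECG, so people aged 60 to 90 can enter with abnormal traces. For anyone abnormal but not clinically significant at screening, the one worsening the grading allows is the one the table cannot show.

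**Working it through.** The plan states no figure to reproduce here. The check is an enumeration of category changes.

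**Inputs.** Collected categories: normal (N), abnormal not clinically significant (NCS), abnormal clinically significant (CS), from Protocol 7.1.4. Reported categories: normal, abnormal, from Protocol 9.4.5.4 and SAP 5.12.5. Baseline is the screening trace. There are 15 subjects per arm and 30 on UB-311 (SAP 5.13).

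**Step 1: possible changes.** Three categories give 3 × 2 = 6 ordered changes. Mapped to the two reported levels:

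| Change as collected | Change as reported | Visible as a change? |
|---|---|---|
| N to NCS | normal to abnormal | yes, but merged with N to CS |
| N to CS | normal to abnormal | yes, but merged with N to NCS |
| NCS to N | abnormal to normal | yes |
| CS to N | abnormal to normal | yes |
| NCS to CS | abnormal to abnormal | no |
| CS to NCS | abnormal to abnormal | no |

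Four of the six remain visible and two are lost. A three-by-three table would show all six separately.

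**Step 2: weight of one case.** One subject moving from NCS to CS is 1/15 = 6.7% of an arm, or 1/30 = 3.3% of all subjects on UB-311.

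**Step 3: how many subjects.** The documents give neither the share abnormal at screening nor a rate of worsening. Purely as an assumption, if 30% to 60% were abnormal at screening, the pool would be 0.30 × 45 = 13.5 to 0.60 × 45 = 27 subjects overall, and 0.30 × 30 = 9 to 0.60 × 30 = 18 on UB-311. Those are subjects in whom a move within the abnormal group is possible, not subjects whose result is mis-tabulated. The latter number cannot be derived.

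**Step 4: other routes by which the change could surface.**

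- *Adverse events (Protocol 7.6).* An ECG abnormality is recorded as an AE if it is symptomatic, needs corrective treatment, leads to discontinuation or meets a seriousness criterion. Protocol 7.5 includes medically important events among those criteria. A CS rating is not itself a trigger.
- *DSMB (Protocol 7.9).* The briefing tables cover shifts and clinical abnormalities and name the ECG. The third and last scheduled meeting follows the 27th subject's final visit, so scheduled reviews need not include complete data on all 45.
- *Listing (SAP 5.12.5).* At full completion this would hold about 45 × 3 = 135 scheduled records. If it shows the three-level grade, every change can be read off, but nothing says that it will.

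**The case against.** The strongest reply is that nothing is lost from the trial record. The CRF holds the grade, a listing is promised, the DSMB sees ECG shifts, and an ECG change that matters clinically will usually qualify as an AE, particularly through the medically important criterion. What remains is narrow: a trace rated clinically significant in someone without symptoms, not treated for it, not discontinued and not judged to have a medically important event. With about 135 records a reader could find such cases by hand. This is also an exploratory trial with no ECG hypothesis, and the synopsis does not name the ECG among its primary safety evaluations.

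Most of that stands and sets the severity. It does not remove the point. A listing with unspecified columns is not a by-arm summary, DSMB material is not the clinical study report analysis, and the AE route leaves a real gap. The SAP is also more detailed elsewhere: it plans shifts from baseline for physical examination (5.7.2) and an unchanged, improved or worsened classification for ARIA (5.12.6).

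One further passage bears on entry. Appendix 1, section 2.1, mentions the screening ECG in a loosely worded sentence requiring screening results free of clinically significant abnormalities. If it applies to the ECG, subjects abnormal at screening would be NCS. That makes CS to NCS unlikely but leaves NCS to CS as their only possible worsening.

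Three stronger readings are tempting and not supported. A reader might infer that ECG worsening goes unrecorded or unreported; the CRF, the listing, the AE route and the DSMB tables contradict that. A reader might infer that the ECG summary cannot show worsening at all; a move from normal to either abnormal grade stays visible. And a reader might infer a conflict between protocol and SAP; they state the same two-level rule.

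**Conclusion.** The point holds as a limitation of the planned summary tables. By-arm change from screening cannot show movement between the two abnormal grades, and it does not separate new trivial findings from new significant ones. This follows from the wording alone and needs no assumption about frequency. It does rest on reading the change summary as built on the two-level status, which is what the word "only" in that rule implies. Two of six category changes are hidden. How many subjects that affects is unknown, and any figure based on an assumed share abnormal at screening describes only the pool at risk. Severity is minor: the data are collected, other routes pick up much of what matters, and the correction is nearly free.

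**What to change.** In SAP 5.12.5, replace the normal/abnormal rule with a shift table by arm on the three collected categories, from screening to Week 52 and from screening to Week 78. Add, by arm, the number and percentage of subjects newly abnormal and clinically significant at any post-baseline ECG. State that the ECG listing will show the three-level grade at each visit. Record the departure from Protocol 9.4.5.4 in SAP section 6.

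The cost is one table and a few lines of SAP text. No extra assessment, CRF change or data collection is needed.

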5.12.6 Imaging-Related Safety Endpoint

Imaging abnormality events will include the following:

- ARIA-E, ARIA-H,
- ARWMC
- PVM, and
- Non-ARIA abnormalities

All ARIA, PVM, ARWMC and non-ARIA abnormalities will be reported and analyzed as image related abnormalities. ARIA, PVM, ARWMC and non-ARIA abnormalities that appear following first administration of treatment will be reported as imaging related treatment- emergent abnormalities.

An abnormality summary table will be provided for baseline and post-baseline visit by:

- all imaging events including ARIA-E, ARIA-H, Non-ARIA, ARWMC, PVM
- by treatment arm
- by treatment arm and visit

Frequency of ARIA (Presence Yes/No) (Total ARIA, ARIA-E only and ARIA-H only) will be provided with number and percent of patients for baseline visit.

Frequency/Patient of ARIA (Total ARIA, ARIA-E only and ARIA-H only) will be summarized for safety population by treatment with number and percent of patients.

New Events (since last visit) will be summarized for safety population by treatment with number and percent of patients.

Improvement since baseline (ARIA-E and ARIA-H) will be summarized for safety population by treatment with number and percent of patients.

PVM/ARWMC/non-ARIA abnormalities will be summarized for safety population by treatment with number and percent of patients.

The number of ARIA-E/ARIA-H abnormalities will be summarized for safety population by treatment with n, mean, std dev, CV, Q1, median, Q3, Min, Max, L95 and U95.

Distribution of number of ARIA-E/ARIA-H abnormalities by actual value, change from baseline will be summarized for safety population by treatment with number and percent of patients.

Visit value and change from baseline for ARIA-E, ARIA-H and total will be summarized for safety population by treatment with mean and standard deviation.

Overall evaluation of change for ARIA-E/ARIA-H frequency by category (unchanged, improved and worsened) will be summarized for safety population by treatment with number and percent of patients.

Number of occurrences ARIA-E/ARIA-H frequency by brain region (FL, PL, TL, OL, Cer, BS, Oth) will be summarized for safety population by treatment with number and percent of patients by visit.

Overall evaluation of change for ARIA- E/ARIA-H frequency by type will be summarized for safety population by treatment with number and percent of patients.

Overall change from baseline for ARWMC frequency by visit will be summarized for safety population by treatment with number and percent of patients.

Visit value and Change from baseline for ARWMC will be summarized for safety population by treatment with n, mean, std dev, CV, Q1, median, Q3, Min, Max, L95 and U95.

Overall change from baseline for post- vaccine meningoencephalitis frequency by visit will be summarized for safety population by treatment with number and percent of patients.

5.13 **Sample Size**

This early phase clinical trial is exploratory in nature; hence, the sample size is determined to assess the primary objective of safety, tolerability, and immunogenicity of UB-311. The total of 45 subjects is planned to be enrolled, 15 per arms. For each UB-311-treated arm, 15 subjects are thought to be sufficient to detect an adverse event with an incidence of 7%. Furthermore, 30 subjects receiving UB-311 are anticipated to be able to detect an adverse event with an incidence of 4%.

With the current sample sizes, there may be limited power to detect a reduction in mean SUVRs or regional SUVRs unless there is a dramatic clearance of pre-existing plaques, and extremely limited power to detect effects on cognitive and functional endpoints. These analyses are therefore considered exploratory.

5.14 **Interim Analysis**

There is no interim analysis for this study.

5.15 **Multiplicity**

There is only primary immunogenicity endpoint in this study, and all efficacy endpoint will be served as secondary endpoint, and p-Value and its confidence interval will be used for screening purpose, so there is no multiplicity adjustment performed.

5.16 **General Conventions for Tables, Listings and Figures**

For summary tables, unless otherwise specified, the number of decimal places provided in the SAS output will be based on the accuracy of the least accurate value in the raw data as follows:

- n integer
- Arithmetic mean 1 decimal place more than the least accurate number in the raw data
- SD 2 decimal place more than the least accurate number in the raw data
- CV(%) 2 decimal places
- Geometric mean 1 decimal place more than the least accurate number in the raw data
- Median 1 decimal place more than the least accurate number in the raw data
- Minimum same number of decimal places as raw data

- Maximum same number of decimal places as raw data
- Confidence interval same number of decimals as the associated statistic
- Geometric mean ratio 2 decimal places

6 **CHANGES FROM THE PROTOCOL TO THIS SAP**

Additional details and specifications have been included in this SAP to allow for better understanding of the intended methods. Additional analyses (including exploratory and subgroup assessments) for select variables have been added. Additional sensitivity analyses will be conducted to explore any effects related to the presence of data outliers.

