#### **Vasogenic edema and amyloid imaging related abnormalities**

The number and percentage of subjects with amyloid-related imaging abnormalities (ARIA) will be summarized and presented by treatment group.

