5 STATISTICAL METHODS

5.1 General

Continuous data will be summarized by treatment group using the number of observations available (n), mean, standard deviation (SD), median, interquartile range (IQR), minimum, and maximum.

Categorical data will be summarized by treatment group using count and percentage. Missing data will not be categorized in the summaries.

In general, descriptive statistics of quantitative efficacy and safety parameters (results and changes from baseline) by scheduled visit will be provided on observed cases, i.e. the inclusion of only subjects with non-missing assessments at a specific visit.

For undetected value, this study will take the minimum value that can be detected as the text value, eg, <3.5 will be treated as 3.5 and <0.012 will be treated as 0.012 when performing the summary and will list the original value in listing.

- The pre-treatment period is defined as the time from the date of the informed consent to the time before the administration of first dose of study medication.
- The post-treatment period is defined as the time from after the first dose of study medication to the end of the study.

All statistical tests will be two-sided at the alpha level of 0.05, unless otherwise specified.

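### The only 95% limits planned for ARIA sit on the mean lesion count, where they fail if ARIA is sparse; the proportion of subjects with ARIA gets no interval

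*SAP*

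**What the plan says.** The protocol synopsis lists ARIA within the primary safety and tolerability endpoint. Protocol 9.4.5.1 plans a count and percentage: "The number and percentage of subjects with amyloid-related imaging abnormalities (ARIA) will be summarized and presented by treatment group".

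SAP 5.12.6 expands this into many summaries, which fall into three groups:

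- **Subjects with ARIA.** "Frequency/Patient of ARIA (Total ARIA, ARIA-E only and ARIA-H only) will be summarized for safety population by treatment with number and percent of patients". The lines for new events, improvement, change category and brain region are also number and percent. None has an interval.
- **Values by visit.** "Visit value and change from baseline for ARIA-E, ARIA-H and total will be summarized for safety population by treatment with mean and standard deviation". No interval.
- **Lesion counts.** "The number of ARIA-E/ARIA-H abnormalities will be summarized for safety population by treatment with n, mean, std dev, CV, Q1, median, Q3, Min, Max, L95". The matching upper limit is listed too. This is the only ARIA line with limits; the other line in that section with L95 and U95 concerns white matter changes.

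SAP 5.1 supplies no interval by default: "Categorical data will be summarized by treatment group using count and percentage". The SAP does plan intervals for proportions elsewhere: a 90% interval for the difference in antibody response rate (4.2) and a one-sided 95% interval for the visual PET read (5.10).

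On size, SAP 5.13 says: "The total of 45 subjects is planned to be enrolled, 15 per arms".

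**The concern.** ARIA-E and new ARIA are likely to be absent or rare in an arm of 15. A symmetric interval around the mean of a count that is zero for most subjects does not behave as a 95% interval. It has no width when every count is zero, and it runs below zero when a few are not. Meanwhile the quantity a safety reader wants, the share of subjects affected and how large that share could really be, has no interval at all.

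At stake is how a clean or nearly clean arm is presented. A row of limits reading 0 to 0 looks like certainty, when 15 subjects can exclude only fairly high risks.

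**Working it through.** **Inputs.** n = 15 per arm and 30 on UB-311 (SAP 5.13). L95 and U95 are read as two-sided 95% limits of the mean, in line with the two-sided 0.05 level in SAP 5.1. The documents give no ARIA incidence or lesion distribution, so the values used below are assumptions.

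**The plan's own safety figures.** SAP 5.13 says "15 subjects are thought to be sufficient to detect an adverse event with an incidence of 7"% and "30 subjects receiving UB-311 are anticipated to be able to detect an adverse event with an incidence of 4"%. With P(at least one event) = 1 − (1 − p)^n:

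- 1 − 0.93^15 = 66.3%
- 1 − 0.96^30 = 70.6%

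No detection probability is stated, so there is no target to match. The figures agree with 1/n rounded up (1/15 = 6.7%, 1/30 = 3.3%). They show that rates near 4% to 7% are of interest to the plan.

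**Limits at n = 15.** Limits of the mean are mean ± t × SD/√15, with t(0.975, 14) = 2.145. The table assumes one lesion per affected subject and sets the exact (Clopper-Pearson) interval for the proportion alongside.

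| Affected | Mean | SD | Limits of mean | Exact 95% for proportion |
|---|---|---|---|---|
| 0/15 | 0 | 0 | 0 to 0 | 0 to 21.8% |
| 1/15 | 0.067 | 0.258 | −0.076 to 0.210 | 0.2 to 31.9% |
| 2/15 | 0.133 | 0.352 | −0.062 to 0.328 | 1.7 to 40.5% |
| 3/15 | 0.200 | 0.414 | −0.029 to 0.429 | 4.3 to 48.1% |
| 4/15 | 0.267 | 0.458 | 0.013 to 0.520 | 7.8 to 55.1% |

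In the first row the CV is 0/0. The exact upper limit there is 1 − 0.025^(1/15) = 21.8%; for 0/30 it is 1 − 0.025^(1/30) = 11.6%.

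Using 1.96 in place of t does not help: the lower limit is still negative at one to three affected (−0.064 at 1/15). More lesions do not help a single affected subject either. With k lesions, both the mean and its standard error are k/15, so the lower limit is (k/15)(1 − 2.145), which is negative for every k. Five lesions give −0.38 to 1.05.

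**Coverage at n = 15.** With one lesion per affected subject, the true mean count equals the incidence p, so both intervals target the same number. Summing binomial probabilities over the outcomes whose interval contains p gives:

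| True incidence (assumed) | No one affected | Negative lower limit | Coverage, limits of mean | Coverage, exact |
|---|---|---|---|---|
| 4% | 54.2% | 45.5% | 45.8% | 98.0% |
| 7% | 33.7% | 64.6% | 66.3% | 98.2% |
| 10% | 20.6% | 73.9% | 79.2% | 98.7% |
| 15% | 8.7% | 73.5% | 90.9% | 98.3% |
| 20% | 3.5% | 61.3% | 96.1% | 98.2% |

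At 7%, the interval either has no width or has a negative lower limit in 33.7% + 64.6%, or about 98%, of arms.

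**Sensitivity to several lesions per subject.** If affected subjects have 1 + Poisson(0.5) lesions (assumed; simulated), coverage of the mean count is about 54%, 79%, 77% and 88% at 5%, 10%, 15% and 20% incidence. Clustering therefore keeps coverage low over a wider range.

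**The case against.** The strongest reply is that these limits belong to a lesion count and are nowhere offered as an interval for ARIA risk. The SAP already plans number and percent of patients with ARIA, new events and the distribution of counts, so anyone who sees 0 of 15 can work out the exact limit. Leaving safety proportions without intervals is the convention for adverse events throughout this plan, the trial is declared exploratory, and no test, stopping rule or decision uses L95 or U95.

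Much of that stands, and it limits the point in four ways:

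- **Meaning of the limits.** A reader might infer that the plan would report an ARIA risk of 0 to 0. The documents do not support that: L95 and U95 are undefined, and they are attached to the number of abnormalities.
- **ARIA-H.** A reader might infer that nearly all counts will be zero. Protocol 4.3 excludes only subjects with more than four microhemorrhages at screening, so ARIA-H counts may start above zero. An illustrative arm with five affected subjects (1, 1, 2, 3 and 4 lesions) gives limits of 0.02 to 1.44. Under the clustered model, coverage is 89%, 92% and 94% when 30%, 40% and 50% are affected.
- **Denominator.** A reader might infer that unscanned subjects are counted as ARIA-free. SAP 5.12.6 names the safety population but does not say this, and Protocol 4.4 provides for an early-termination MRI when applicable. SAP 5.12.3 and 5.12.4 do require a post-treatment value for laboratory and vital-sign summaries, so stating the rule for MRI is a clarification.
- **Consequence.** This is a matter of reporting. Sample size, conduct and decision rules are untouched.

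What does not stand is the suggestion that nothing needs changing. The one ARIA interval planned breaks down for sparse counts, and a prespecified interval for a primary safety item should not be left for readers to derive.

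**Conclusion.** The point holds as a reporting defect. If L95 and U95 are limits of the mean, then with 15 per arm and sparse ARIA they have zero width or an impossible lower bound in most arms. With one lesion per affected subject they cover the true mean about 46% to 79% of the time at assumed incidences of 4% to 10%, against at least 98% for exact limits on the proportion. By 20% incidence with single lesions, coverage is no longer short, although negative lower limits remain common.

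The conclusion rests on three assumptions: the reading of L95 and U95, the assumed incidences, and the assumed lesion pattern. It applies most directly to ARIA-E and treatment-emergent ARIA, and least to total ARIA-H. It does not show that the plan misreports ARIA risk. It shows that the plan gives no precision for that risk, and that the only ARIA precision it does give is unreliable where ARIA is rare.

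**What to change.** In SAP 5.12.6:

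1. Drop CV, L95 and U95 for the ARIA-E and ARIA-H counts. Keep median, minimum and maximum.
2. Add exact (Clopper-Pearson) 95% confidence intervals to the number and percent of subjects with treatment-emergent ARIA-E and, separately, ARIA-H, for each arm and for the two UB-311 arms pooled.
3. State the denominator for these percentages as subjects with at least one post-baseline MRI.

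The cost is SAP wording and a table shell. No visit, scan or sample-size change follows. The stated uncertainty becomes wider: an arm with no ARIA would show 0 to 21.8%, and 30 pooled UB-311 subjects with none would show 0 to 11.6%.

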#### **4.4 Subject Withdrawal Criteria**

A subject may withdraw from the study treatment or the study due to the following reasons:

1. Lost to follow up.
2. The subject withdraws consent.
3. Development of an imaging abnormality consistent with vasogenic edema, macrohemorrhage, or an area of superficial siderosis appears or a clinically symptomatic microhemorrhage.
4. Development of intolerable adverse event due to study treatment as determined by the investigator and/or subject.
5. Development of an intercurrent illness or condition for which the subject requires concomitant medications which are not allowed in the study.
6. Discovery that the subject entered the study in violation of the protocol or occurrence of a protocol violation during the study that may affect safety at the investigator's discretion.

7. Subject's pregnancy.
8. Subject's death.
9. The investigator feels that in the best interest of the subject's health, the subject is to be withdrawn from the trial.
10. Data not known before starting the trial become available and raise concern about the safety of the study drug such that continuation would pose potential risk to any particular subject.

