### **The type and timing of the data to be collected and follow-up for withdrawn subjects**

When a subject decides to withdraw from the study treatment or the study, he/she should be contacted to obtain information about the reason(s) for discontinuation and any adverse events. For subjects who withdraw from the study treatment or the study after study drug administration, efforts will be made, as appropriate and at discretion of investigator, to have an early termination (ET) visit arranged as soon as possible. All study procedures listed in Visit 13/ET (see sections 8.2 and 8.3) should be completed at the early termination visit when applicable, including: ECG, physical examination, vital signs, clinical chemistry and hematology tests, serum anti-A $\beta$  antibody level evaluation, recordation of any AE/SAE, concomitant treatments (medications/therapy), imaging evaluations (18F-AV-45 PET and MRI), and neuropsychological tests (including MMSE, CDR-SB, ADAS-Cog, ADCS-ADL, and NPI). In addition, subjects will be encouraged to complete all remaining scheduled visits and procedures before the early termination visit.

If a subject is withdrawn at a scheduled study visit, the early termination visit could be conducted on the same day. Besides, in the event of a drop-out after study drug administration, all attempts should be made to follow-up the subject through telephone calls or by direct contact until the end of this study (Week 78), in order to document any delayed adverse drug reactions or adverse events.

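### By-visit ARIA means use only subjects scanned at that visit, while several ARIA findings are listed reasons to leave, so late ARIA burden can be understated

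*SAP*

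**What the plan says.** ARIA is a named component of the primary safety endpoint (Protocol synopsis; Protocol 7.1). MRI is scheduled at screening and at Weeks 12, 24, 36, 48, 60 and 78 (Protocol 7.1.5).

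SAP 5.12.6 lists many ARIA summaries. The one at issue reads: "Visit value and change from baseline for ARIA-E, ARIA-H and total will be summarized for safety population by treatment with mean and standard deviation". It carries no rule for missing scans. SAP 5.1 supplies the general rule: "In general, descriptive statistics of quantitative efficacy and safety parameters (results and changes from baseline) by scheduled visit will be provided on observed cases", which it explains as "the inclusion of only subjects with non-missing assessments at a specific visit". Section 5.12.6 makes no exception to this. The missing-data section, SAP 5.2, deals with partial dates and single missing ADAS-Cog items, not with missed scans. The sensitivity analyses added in SAP section 6 concern outliers.

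Protocol 4.4 begins "A subject may withdraw from the study treatment or the study due to the following reasons", and its third reason is "Development of an imaging abnormality consistent with vasogenic edema, macrohemorrhage, or an area of superficial siderosis appears or a clinically symptomatic microhemorrhage". For subjects who withdraw after dosing, the Protocol asks for an early-termination visit that includes MRI where applicable, at the investigator's discretion. It also says they will be encouraged to complete the remaining visits. The schedule in Protocol 8.2 labels the last column 78/ET. Neither document says at which visit an early-termination MRI is counted in the by-visit tables.

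SAP 5.12.6 also plans a per-patient ARIA frequency on the safety population, a table of new events since the last visit, and reporting of abnormalities that first appear after dosing as treatment-emergent. No summary is defined on a subject's worst post-baseline scan.

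**The concern.** The quantity being averaged is also a listed reason for leaving the average. A subject who develops vasogenic edema or superficial siderosis at Week 24 and then leaves the study contributes nothing to an observed-case mean at Week 48 or 60, even if the lesion is still there. Missing scans can therefore depend on the outcome, and the SAP has no rule that addresses this.

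The late visits matter because Protocol 5.2 escalates exposure by adding injections, the last at Week 60. A reader will look at ARIA burden from Week 48 onward to judge whether it accumulates with repeated dosing. If the arm with more ARIA also loses more of its affected subjects, its late means move toward those of the other arms, and the table can look like absence of accumulation. With 15 subjects per arm, one or two departures are enough to change the picture. A by-visit mean alone cannot separate resolution in subjects who stay from departure of those affected.

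**Working it through.** The documents give no ARIA rate, no lesion count and no withdrawal rate, so there is no planned figure to reproduce. The calculation below shows the mechanism under stated assumptions.

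**Inputs**
- Arm size: 15 (Protocol 9.1; SAP 5.13).
- q, the share of an arm with new ARIA: 7% and 20%, assumed. The 7% is borrowed from the adverse-event incidence in the sample-size section and is not an ARIA rate.
- L, the mean number of lesions per affected subject: 3, assumed, with lesions persisting to Week 78.
- Background lesions: none at first, then an average of 1.0.
- w, the share of affected subjects with no scan counted at Week 78: 0, 0.5 or 1, assumed.

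**Formulas**
- Mean if everyone is scanned = q × L.
- Observed-case mean = q × (1 − w) × L / (1 − q × w).

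**No background lesions**
- w = 0: the two means are equal and there is no bias.
- q = 0.07, w = 0.5: full mean 0.07 × 3 = 0.21; observed-case mean 0.105 / 0.965 = 0.11; about 48% low.
- q = 0.20, w = 0.5: full mean 0.20 × 3 = 0.60; observed-case mean 0.30 / 0.90 = 0.33; about 44% low.
- w = 1: the observed-case mean is 0 in both cases.

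**Check on one arm of 15, one lesion per affected subject, 3 affected**
- Everyone scanned: 3 / 15 = 0.200.
- Half of those affected unscanned (an average over arms): 1.5 / 13.5 = 0.111.
- All affected unscanned: 0 / 12 = 0.000.
- Proportion ever having ARIA: 3 / 15 = 20% in every case, because a detected event stays counted.

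**With background microhemorrhages**

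Protocol 4.3 excludes subjects with more than four microhemorrhages, so up to four are allowed at entry. Assume an average of 1.0 in all 15 subjects, and two affected subjects with 3 extra lesions each.
- Visit value, everyone scanned: (13 × 1 + 2 × 4) / 15 = 1.40.
- One affected subject unscanned: (13 + 4) / 14 = 1.21, about 13% low.
- Both unscanned: 13 / 13 = 1.00, about 29% low.
- Change from baseline: 6 / 15 = 0.40 with everyone scanned, 3 / 14 = 0.21 with one unscanned, 0 with both unscanned.

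Background lesions thus soften the relative loss in visit values but not in changes from baseline.

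**Effect of the early-termination scan**

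If leavers have an early-termination MRI and it is counted at Week 78, persistent lesions return to the Week 78 mean and w falls toward 0 there. Missed scans at Weeks 48 and 60 remain missing. The SAP does not say which treatment of these scans applies.

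**The case against.** A reader might infer that ARIA is summarised only on subjects still scanned, and that late values will fall because affected subjects have gone. The documents do not support either statement.

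- **Other tables keep these subjects.** Per-patient frequency, new events and treatment-emergent reporting in SAP 5.12.6 retain anyone whose ARIA was detected before leaving. This stands. Those tables give incidence, however, not lesion burden.
- **The observed-case rule is narrower than it looks.** SAP 5.1 applies it in general, to quantitative parameters by scheduled visit. The lesion-count table, and the one described by "Overall evaluation of change for ARIA-E/ARIA-H frequency by category (unchanged, improved and worsened) will be summarized", are not stated to be by visit. This stands, so the point is confined to the visit-value and change-from-baseline means.
- **Leaving is not automatic.** Withdrawal is permissive and may be from treatment only. An early-termination MRI is asked for and further visits are encouraged. Asymptomatic microhemorrhage is not a listed reason, so part of ARIA-H does not follow this route. All of this stands: the documents show a risk of bias, not a certain fall. ARIA-E may also resolve in subjects who stay, so a fall would not by itself show attrition.
- **Attrition would be visible.** SAP 5.1 lists n for continuous summaries, and discontinuations are tabulated with reasons. The ARIA tables are descriptive, with no decision rule attached. This lowers the stakes. But no planned table is described as linking departures to ARIA visit by visit.
- **The size rests on unfavourable assumptions:** persistent lesions, no background, and no Week 78 scan in leavers. This stands, and the figures are illustrations only.

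**Conclusion.** The by-visit ARIA means and changes from baseline are open to outcome-dependent missingness, and the SAP neither addresses it nor says where early-termination scans are counted. The likely direction is understatement of late burden. If half of the affected subjects are unscanned at Week 78, the illustrated mean is 0.11 against 0.21 (7% affected) or 0.33 against 0.60 (20% affected). This assumes 15 per arm, persistent lesions averaging 3, no background lesions and no Week 78 scan in leavers. With an average background of 1.0 and two affected subjects with 3 extra lesions each, the loss in visit values is about 13% to 29%. If affected subjects continue to be scanned, the bias is zero.

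ARIA incidence is not at risk in the same way, because the per-patient tables keep a subject with a detected event. This is a cheap and worthwhile improvement to the burden tables, not a defect that undermines ARIA reporting as a whole.

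**What to change.** In SAP 5.12.6:

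1. Add a summary by arm of each subject's worst post-baseline ARIA-E and ARIA-H count and its change from baseline, over all post-dose scans, including unscheduled and early-termination MRIs.
2. Keep the by-visit tables, and show at each visit the number scanned and the cumulative number who have left after ARIA.
3. State at which visit an early-termination MRI is counted.

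Do not redefine the improved/unchanged/worsened category by the worst scan. That would make improvement almost unreachable and would conflict with the improvement-since-baseline summary already planned in the same section.

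The cost is SAP wording and one or two extra tables from scans already collected. A worst-scan summary does not show resolution, which is why the by-visit tables should stay. It is also cut short by withdrawal, since a subject who leaves early has fewer scans from which a worst can be taken. It should be read beside the numbers scanned.
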